5.3. Harms

We will report descriptively the number of adverse events, serious adverse events and the number of each judged to be related to the therapy, and rates of reliable deterioration. Instances of adverse events will be reviewed throughout the trial by the chief investigator (and the TSC and sponsor if required according to the relevant SOPs), following the relevant SOPs with regard to classification, response and reporting.

6. Abbreviations and definitions

Abbreviation	Meaning	Detail
SAP	Statistical Analysis Plan	
SOP	Standard Operating Procedures	SOPs document a series of steps to be followed to accomplish a process. They include the purpose and scope of a process, describes procedure (i.e. what, where, and when), assigns responsibility for action and decisions (i.e. who), identify records to be kept, and identify associated and reference documents (as applicable)
TSC	Trial Steering Committee	The role of the TSC is to provide overall supervision for a study on behalf of the Sponsor and Funder and to ensure that the project is conducted in line with regulatory requirements and to the rigorous standards set out in the Department of Health's Research Governance Framework for Health and Social Care and Guidelines for Good Clinical Practice.

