2.1. Design

Two cohort randomised multiple baseline ABA case-series design. Randomisation is to a wait period of 3,4 or 5 weeks before starting therapy. The intervention is an adapted form of behavioural therapy delivered on a one-to-one basis over up to 22 sessions, over up to 7 months.

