2.3. Sample Size

It is good practice to have at least 3 replications of the pattern of change across different cases (inter-case replication) as well as more than one therapist treating patients. Patients are treated in two cohorts within the current study: a total of 12 participants, 6 in each cohort, would allow these criteria to be met within each cohort (with at least two therapists seeing patients in each cohort).

Participants who exit the study after randomisation, but before completing the pre-therapy measures will be replaced (with new random allocation) to give N=12 commencing the therapy period.

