5.1. Outcome definitions

Means of assessing primary (feasibility) outcomes

1. Safety will be measured by rates of therapy-related adverse events across the study period, and rates of reliable deterioration from the pre-treatment point on the Patient Health Questionnaire (PHQ), Altman Scale for Rating Mania (ASRM), Affective Lability Scale (ALS), Generalised Anxiety Disorder questionnaire (GAD), Quality of Life in Bipolar Disorder scale (QoL.BD) and Bipolar Recovery Questionnaire (BRQ) at 7 months (30 weeks) follow-up.
2. Acceptability will be measured by therapy uptake and completion rates across the study period, and quantitative and qualitative feedback from participants and therapists at the post-therapy point.
3. Potential of the intervention to deliver benefit will be measured by rates of reliable, and reliable and clinically significant, change in the Patient Health Questionnaire and the bipolar-depression scale of the Affective Lability Scale, from the baseline period (mean score) to the 3 week post-therapy period (mean score).

Secondary outcome measures

1. Rates of reliable, and reliable and clinically significant, change on the following measures: Bipolar Disorder Recovery Questionnaire, Quality of Life in Bipolar Disorder Scale and Generalised Anxiety Disorder assessment scale from pre-therapy to 7-month follow-up.
2. Rates of reliable, and reliable and clinically significant, change on the Altman Scale for Rating Mania from the baseline period (mean score) to the 3 week post-therapy period (mean score).
3. Group-level change in PHQ, ALS, ASRM, BRQ, QoL.BD, GAD from baseline to 6-month follow-up and pre-therapy to 7-month follow-up.
4. Mood instability will be measured (in addition to the ALS) by a visual analogue scale of mood at five timepoints per day for 14 days on two occasions (pre and post therapy) for each participant. This allows for the calculation of mood instability before and after therapy.

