5.2. Analysis methods

In relation to aim (i) which concerns safety, feasibility and acceptability, we will report descriptively the number of adverse events, serious adverse events and the number of each judged to be related to the therapy, and rates of reliable deterioration. We will also report the number of participants experiencing at least one adverse event. We will report the number of participants expressing an interest in the study, giving consent, found to be eligible, commencing treatment and completing treatment, as well as the median, mode and range of sessions attended during treatment. We will report descriptively the average and distribution of scores on the therapy feedback items.

Aim (ii) investigates the potential for clinical efficacy. Analytical approaches to examining clinical outcome data in a case series can include visual and statistical methods, and focus on change at the

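### Adverse events are reported only as study-wide totals: no split by phase, no exposure and no denominator for the primary safety rate, so no event output shows whether events are more frequent on therapy than before it

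*SAP*

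**What the plan says.** Section 5.1 of the SAP lists safety as the first primary outcome: "Safety will be measured by rates of therapy-related adverse events across the study period, and rates of reliable deterioration from the pre-treatment point". The deterioration part covers six scales (PHQ, ASRM, ALS, GAD, QoL.BD, BRQ) and is read at 30 weeks.

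Section 5.3 describes the event output: "We will report descriptively the number of adverse events, serious adverse events and the number of each judged to be related to the therapy". That sentence goes on to include rates of reliable deterioration. Section 5.2 repeats the same list and adds: "We will also report the number of participants experiencing at least one adverse event".

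The design in section 2.1 is a "Two cohort randomised multiple baseline ABA case-series design". The first phase is untreated: "Randomisation is to a wait period of 3,4 or 5 weeks before starting therapy". Section 5.2 has weekly symptom scores examined across the baseline, therapy and post-therapy periods. It gives no such instruction for adverse events.

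On review of events, section 5.3 says: "Instances of adverse events will be reviewed throughout the trial by the chief investigator". The steering committee and sponsor take part if required, and classification follows SOPs.

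**The concern.** The design observes each participant untreated before therapy starts, and the SAP uses that period for symptom scores. For adverse events the period is not used. The planned numbers are totals, related totals and a count of people affected, all without time at risk.

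Two problems follow. First, section 5.1 speaks of rates but does not say whether they are per participant, per participant who started therapy, or per unit of time, nor when event counting ends. Second, a total that mixes phases cannot show whether events of any cause became more frequent once therapy began. Within the event data, the only element tied to therapy is the case-by-case judgement of relatedness. An increase in events that reviewers put down to the underlying disorder would not stand out in any planned adverse-event output.

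Safety is a primary outcome, and section 2.4 says that the progression rules exist to avoid taking forward a therapy likely to be unsafe or unacceptable.

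**Working it through.** The SAP gives no event rate, person-time or safety precision, so there is no figure of its own to reproduce. Exposure can be built from its durations.

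**Inputs**
- Participants: 12 starting therapy (2.3: "to give N=12 commencing the therapy period").
- Wait: 3, 4 or 5 weeks (2.1), allocated 1:1:1 with one block per cohort of 6 (2.2), so 4 people per wait length.
- Therapy: up to 7 months (2.1), taken as 30 weeks as in Table 2.6.1.
- Post-therapy: 3 weeks of monitoring (1.1), or 26 weeks to the last scheduled contact (Table 2.6.1). The SAP does not say which applies to adverse events, so both are shown.
- Assumptions: full retention and maximum therapy length.

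**Person-weeks by phase**
- Wait: 4 × (3 + 4 + 5) = 48.
- Therapy: 12 × 30 = 360, which is 360/48 = 7.5 times the wait.
- Post-therapy: 12 × 3 = 36, or 12 × 26 = 312.

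| Event window ends | Total | Wait | Therapy | Post-therapy |
|---|---|---|---|---|
| 3 weeks after therapy | 444 | 10.8% | 81.1% | 8.1% |
| 26 weeks after therapy | 720 | 6.7% | 50.0% | 43.3% |

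Between 19% and 50% of the pooled time therefore lies outside the main therapy phase. With the longer window, most of that is post-therapy time, not the wait.

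**Effect of the missing denominator.** The same number of related events divided by 360 person-weeks (therapy only) or by 720 (all phases to 26 weeks) gives rates that differ by a factor of 720/360 = 2.

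**Effect of pooling.** If the rate on therapy is R times background, the pooled rate relative to background is (wait + R × therapy + post) / total.
- R = 2, 3-week window: (48 + 720 + 36)/444 = 1.81.
- R = 2, 26-week window: (48 + 720 + 312)/720 = 1.50.
- R = 3: 2.62 and 2.00 respectively.

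The dilution is moderate. The larger difficulty is that background is not reported, so there is nothing to set the pooled figure against.

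**Why a split needs person-time.** Take a hypothetical 18 events on therapy and 2 in the wait. The counts differ ninefold, but 18/360 = 5.0 and 2/48 = 4.2 per 100 person-weeks.

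**What a split can deliver.** An exact conditional Poisson comparison of therapy with wait (one-sided 0.025) was calculated for assumed background rates, which are not in the SAP:

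| Assumed events per person-week | Expected events in wait | Power for a doubling | Power for a tripling |
|---|---|---|---|
| 0.02 | 1.0 | about 0% | 2% |
| 0.05 | 2.4 | 10% | 39% |
| 0.10 | 4.8 | 28% | 79% |

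The table would be descriptive only.

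**The case against.** The strongest reply is that safety does not rest on event counts alone. A reader might infer that the relatedness judgement is the only therapy-specific safety signal left. The SAP does not support that. Section 5.1 puts reliable deterioration on six scales into the same primary outcome, starting at the pre-treatment point, so the wait is excluded and no opinion on cause is needed. Section 5.2 also has two independent raters classify each participant's weekly course, with deterioration as one category. Worsening mood, the change most easily blamed on the disorder, is therefore followed by phase.

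This stands, but it does not replace event data. The deterioration rate compares two time points, so an episode that resolves before week 30 can be missed. It uses observed data only (3.3), so a participant without follow-up drops out. Neither signal counts events that the scales do not measure.

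A reader might also call the relatedness judgement unmasked. The SAP says nothing on masking. Every participant is offered therapy, so there is no arm to mask, and the procedure is left to SOPs. Nor do all the event counts carry an explicit study-wide window: that phrase appears only in 5.1, for therapy-related events. The window itself may be set in the protocol.

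Finally, the gain in precision is small. In the 18 v 2 example the exact 95% intervals are 3.0 to 7.9 on therapy and 0.5 to 15.1 in the wait, per 100 person-weeks. The rate ratio of 1.2 has an interval of about 0.29 to 10.7. These intervals treat events as independent, although a few people may contribute several each. Section 3.1 deliberately limits inference. This is a good reason to keep the table descriptive, but not a reason to leave it out.

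**Conclusion.** The point holds as a reporting gap in the adverse-event output. Events are to be shown without phase or exposure, and the primary safety rate has no denominator, in a design whose phases differ 7.5-fold in length between wait and therapy. It does not show that the plan lacks other safety signals.

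The importance is moderate. Depending on the event window, therapy makes up 50% to 81% of pooled person-time. These figures assume 12 people retained throughout and the maximum therapy length; shorter therapy would lower the 360. The 48 wait-weeks leave out anyone who exits before the pre-therapy measures and is replaced under section 2.3. The post-therapy period is not purely untreated either, because Table 2.6.1 shows that booster sessions take place in it. At the interim review of one cohort the wait would supply only 2 × (3 + 4 + 5) = 24 person-weeks, so the split should not be presented as a progression test.

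**What to change.** Amend sections 5.1 to 5.3 as follows.

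1. State the adverse-event window (start and end) and the denominator of the therapy-related rate, or refer to the protocol section that fixes them.
2. Tabulate all adverse events and serious adverse events, whatever their judged relatedness, by phase of onset: wait; therapy up to the last non-booster session; post-therapy including boosters. For each phase give the number of events, participants affected, person-weeks actually observed, and events per 100 person-weeks. Place the therapy-related counts alongside.
3. List separately any events in people who were randomised but never started therapy. Section 3.3 already separates these people for attendance data, but not for harms.
4. Say that the table is descriptive, that the wait is short, and that therapist contact may lead to more events being detected during therapy than before it.

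The cost is one more table. It needs onset dates for events and the date of each participant's last non-booster session, which are assumed to be recorded. No new assessment or extra participant is required.
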